Toxicant exposure and harm perceptions in cigarette smokers who use or do not use e-cigarettes

ClinicalTrials.gov Identifier: NCT03511001

04/23/2018

TOXICANT EXPOSURE AND HARM PERCEPTIONS IN CIGARETTE SMOKERS
WHO USE OR DO NOT USE E-CIGARETTES

STUDY PROTOCOLS & PROCEDURES

- I. Introduction
- II. Study Sites
- III. Study Personnel
- IV. Participant Recruitment
- V. Participant Screening and Enrollment
- VI. Study Design and Timeline
- VII. Participant Retention
- VIII. Laboratory Procedures and Sampling
- IX. Laboratory Analysis
- X. Study Visits Overview
- XI. Study Questionnaires
- XII. Data Management
- XIII. Recording and Reporting of Adverse Effects

I. Introduction

This study, **Toxicant Exposure and Harm Perceptions in Cigarette Smokers Who Use or Do Not Use E- Cigarettes** is funded by the National Institutes of Health and registered on ClinicalTrials.gov.

Document Purpose

This document is intended to detail all relevant study protocols and procedures. Given rapid advancement in the understanding of the effects of smokers switching to electronic cigarettes, particularly on toxicant exposure (our primary outcome), we considered how to maximize the scientific contribution of the project. The body of work on the use of electronic cigarettes for risk reduction has been conducted with the general population and is now moving into vulnerable populations who carry a substantial disease burden from smoking. The investigative team is uniquely positioned to create progress in the field by examining the research questions with ethnically diverse populations who face significant barriers to smoking cessation. A commitment was made at the San Diego site to enroll Latinx smokers and to offer the study in Spanish in order to address the research questions with an under-studied population. NIH prior approval and Institutional Review Board (IRB) approval was granted to add the University of Kansas Medical Center as a study site to enroll African American smokers. This change enhances the ethnic diversity of enrolled participants as well as expands the science on risk reduction. The second study site (University of Kansas Medical Center) agreed to rely on the IRB of the primary institution (CSUSM).

Additionally, because this project was funded on the first round, reviewer comments were addressed in the implementation of the study protocol post-proposal. These changes impacted inclusion/exclusion criteria and the length of the intervention period. There were no changes to aims, hypotheses, or sample size.

The following Project Summary reflects our implemented protocol and contains an updated premise reflecting the ethnic minority population focus.

Project Summary

This proposal addresses a critical gap in the research regarding the use of electronic cigarettes (ECs) for harm reduction by ethnic minority smokers. Smokers cite reducing perceived harm from smoking as a leading reason for using ECs, and ECs have been suggested by tobacco researchers as a potential harm reduction vehicle for smokers who cannot or will not achieve smoking cessation. The National Academies of Science concluded that ECs pose significantly less exposure to toxicants and less short-term health risks than combustible cigarettes. However, smokers with less education and from ethnic minority backgrounds are less likely to switch to exclusive EC use. Socioeconomic disparities in switching to ECs will perpetuate a greater burden of tobacco-related death and disease among disadvantaged populations. As a human behavioral EC study in which toxicant exposure via the tobacco-specific nitrosamine, NNAL, a highly potent pulmonary carcinogen will be measured, this project addresses a critical barrier in the

field and advances science on the widely used practice of EC use for harm reduction among the two largest ethnic minority groups in the US, Latinx and African Americans. Furthermore, this will be among the first studies to determine how uptake of ECs affects cognitive-perceptual factors involved in sustained tobacco use, such as risk perceptions, utility of smoking, self-efficacy to quit, and tobacco dependence among under-represented minority smokers. This study is directly relevant to the NIH's mission to address cancer risk factors and supports the long-term objective to reduce the disease burden of tobacco use. In the current proposal, Latinx ($n=90$) and African American ($n=90$) cigarette smokers will be randomized in a 2:1 fashion to an EC group ($n=60$ per racial/ethnic group; $N=120$) or an assessment-only control group ($n=30$ per racial/ethnic group; $N=60$). Those randomized to EC will receive a 6-week supply of a fourth generation EC starter kit with their choice of liquid flavor from a standard list. Those randomized to assessment only ($n=60$) will not be provided with an EC. Tobacco consumption in both groups will be assessed at weeks 0 (baseline), 2, and 6. Changes in toxic exposure (NNAL, a primary lung carcinogen and the primary outcome) and carbon monoxide (CO) will be measured from baseline to week 6. Planned covariates include study site, gender, income, tobacco dependence score, and mental health symptoms.

Aim 1. To characterize the toxic exposure of cigarette smokers randomized to the EC group compared to cigarette smokers randomized to assessment-only controls

Hypothesis 1: It is hypothesized that toxicant exposure from baseline to week 6 will be significantly lower in the EC group compared to the assessment-only group.

Hypothesis 2: It is hypothesized that change in cigarette consumption in the EC group from baseline to week 6 will be associated with reduction in toxicant exposure from baseline to week 6.

Aim 2. To assess the effects of uptake of e-cigarettes on perceptions of harm and utility of products

It is hypothesized that from baseline to week 6, the EC as compared to control arm a) will have decreased perceptions of harm to their health from current tobacco use, b) will increase positive utility of EC and increase negative utility of cigarette products, and c) will have decreased expectations of the difficulty of quitting cigarette smoking.

Aim 3. To understand patterns of tobacco product consumption among smokers switching to electronic cigarettes

Changes in tobacco product consumption (cotinine-verified), subjective effects of smoking, and levels of tobacco dependence from baseline to week 6 will be examined in the EC group and baseline predictors of those patterns, including demographic, smoking history, and psychosocial characteristics will be identified.

This project will advance science on the widely used practice of EC use for harm reduction by examining change in toxicant exposure via NNAL and change in cognitive-perceptual variables among African American and Latinx smokers switching to EC compared to smokers who continue to use cigarettes alone. Study findings will have major public health implications, particularly for smokers who have experienced difficulty in quitting cigarettes and for whom EC use as a harm reduction strategy has been considered. The study will enhance the research environment at the PI's university which is classified as

PROJECT SWITCH Protocol

NIH PROJECT #5SC3GM122628-02; CLINICALTRIAL.GOV IDENTIFIER: NCT03511001

both a Hispanic Serving Institution and an Asian American-Native American-Pacific Islander Serving Institution.

Important Terms and Abbreviations

NNAL	4-(methylnitrosamino)-1-(3-pyridyl)-1-butanol
REDCap	Research Electronic Data Capture
CO	Carbon Monoxide
TLFB	Timeline Followback

II. Study Sites

1. San Diego
 - a. California State University San Marcos – [name]
 - b. San Diego State Research Foundation – [name]
 - c. Neighborhood Healthcare, Behavioral Health – [name]
2. Kansas City – Swope Medical Center – [name]

III. Study Personnel

Name	Organization	Role
[name], MPH	California State University San Marcos	Principal Investigator
[name], MPH, MS	Brown University	Co-Investigator
[name]	University of Kansas School of Medicine	Co-Investigator
[name], MA	University of Kansas Medical Center	Project Manager
[name], BA	University of Kansas Medical Center	Lead Researcher
[name], BA	University of Kansas Medical Center	Research Assistant
[name], BA	California State University San Marcos	Project Manager
[name], BA	California State University San Marcos	Research Assistant
[name], BA	California State University San Marcos	Research Assistant

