Sample Size. We estimated our sample requirements using power analyses for primary aims to characterize the reduction in toxic exposure of cigarette smokers randomized to the e-cigarette group compared to cigarette smokers randomized to assessment-only controls (Aim 1:H1) from baseline to week 6 will be significantly lower in the EC group compared to the assessment-only group. Empirical power estimates were assessed by generating multivariate random samples that were matched to the expected response patterns for smokers in control and switching arms with each condition using the same correlation structure of assessments over time as observed in a previous study. In the switching condition we expect larger effects ($d=-0.67$) on primary outcomes (NNAL) for the ~40% of smokers able to switch more completely relative to smokers partially switching ($d=-0.16$). With no change expected in control, we powered primary outcomes for end-of-treatment analyses using an average of effects given 30% of switching smokers with large and 70% with small effects. With a median effect of -0.37 ($SD=0.11$) across 1000 data sets, simulations revealed that the planned design would provide greater than 0.82 power for detecting the treatment differences with a sample of 180 subjects, with an allowance for up to 20% attrition. For Aim1: H2 we will have power to detect moderate effects of changes in cigarette consumption on change in toxicants. In published effects of differences in consumption levels on nitrosamines, 77 differences in consumption (20 vs 10 cig/day) reflected mean difference in log NNAL of $2.60-2.35=0.24$ and effect sizes with $d=0.48$ after 10 weeks 78. We estimate adequate power >0.80 given expected cigarette reductions. Changes in cognitive measures (Aim 2) including decreased perception of harm, average differences in utility of combustible and EC, and increased self-efficacy for quitting are expected to be moderately associated with EC use. Empirical power analyses using regression models of change in cognitive measures over 1000 simulated data sets support the ability to detect moderate effects ($d>0.30$) using a standardized difference in means of cognitive measures with power >0.80 .

V. Participant Screening and Enrollment

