Spirometer measures include: (1) forced vital capacity, FVC (2) Forced expiratory volume in one second, FEV1 (3) The percentage of the FVC expired in one second, FEV1/FVC% (4) peak expiratory flow, PEF (5) Forced expiratory flow over the middle one half of the FVC, FEF25-75%.

Saliva sampling. Saliva sampling is an exploratory addition to this study and will be taken from ten San Diego participants at baseline and week 6. The decision to take saliva sampling in San Diego resulted in an increase from the original $n=90$ to an $n=94$. Samples will be frozen and transported the testing facility on dry ice.

Nasal swab sampling. Nasal swab sampling is an exploratory addition to this study and will be taken from twenty Kansas City participants at baseline and week 6. The decision to take nasal swab sampling in Kansas City resulted in an increase of two participants for a final $n=92$. Samples will be frozen and transported the testing facility on dry ice.

Urine sampling. Urine will be collected at all lab visits and refrigerated until aliquoting. Participants will be instructed to provide at least half of the specimen cup of urine (about 60mL). Participants will be offered water at the beginning of lab sessions to help facilitate sampling.

Urine will be processed by aliquoting the sample into two smaller samples, each 15 mL. One sample will test for cotinine and need to be pre-treated with sodium bisulfate to obtain a pH between 2 and 3. The second sample will test for NNAL and will receive no additional treatment. Both samples will be frozen and stored at $-20\text{ }^{\circ}\text{C}$ before shipping with dry ice for testing.

A urine log will provide the following information for each urine sample: (1) participant ID (2) study time point (3) date: mm/dd/yyyy (4) testing for: NNAL or cotinine. Each lab visit will produce two samples stored for further testing.

Although urine will be taken at all three lab visits, only baseline and week 6 urine will be sent for testing. In the case of missing week 6 samples, week 2 samples will be sent instead as a method of imputation.

Sample shipment. Specimens will be transported in a leak-proof Styrofoam container in leak-proof secondary packaging, with absorbent material placed at the bottom and sides of the container for absorption. 10-15lbs dry ice will be used to maintain storage temperature during transport.

IX. Laboratory Analysis

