Urine: cotinine ng/mL, creatinine mg/mL, nitrosamine 4-(methylnitrosamino)-1-(3-pyridyl)-1-butanol (NNAL) pg/mL, and 3-hydroxycotinine ng/mL

Saliva: Cytokine Panel and C-Reactive Protein

Nasal Swab: MMP9 ELISA in pg/mL and TGF-B1 ELISA in pg/mL

X. Study Visits Overview

Baseline	Week 1	Week 2	Week 4	Week 6
Participant consent	Follow-up check-in	Urine test	Follow-up check-in	Saliva sample (San Diego)
Saliva sample (San Diego)	Yesterday tobacco use	Blood pressure test (must be less than 160/105)	Yesterday tobacco use	Urine test
Complete contact sheet		Carbon monoxide test		Blood pressure test
Blood pressure test (must be less than 160/105)		Eligibility check		Carbon monoxide test
Carbon monoxide test (must be greater than 5 ppm)		Follow-up check in sheet (EC group)		Nasal swab (Kansas City)
Nasal swab (Kansas City)		Timeline follow back		Weight
Final eligibility check and Study ID assignment		Spirometry test		Follow-up check in sheet (EC group)
Randomization		Week 2 survey		Timeline follow back
Charge JUUL (EC group)		Collect used JUUL pods (EC group)		Spirometry test
Timeline follow back		Provide more JUUL pods (EC group)		Week 6 survey
Pod count form (EC group)		Schedule visits/phone calls		Collect used JUUL pods (EC group)
Height and weight		Compensation		Tobacco cessation referral
Baseline survey part 1				Exit survey
Spirometry test				Compensation
Baseline survey part 2				
Cigarette questions and breathing conditions				
E-cigarette switching fact sheet (EC group)				
E-cigarette use instructions (EC group)				
E-cigarette trial and subjective effects questionnaire (EC group)				

Baseline action planning (EC group)				
Schedule visits/phone calls				
Reimbursement schedule				
Urine test				
Compensation				

Table 3. Surveys and tests by study timepoint.

At each lab visit, participants will receive compensation and sign a receipt. At the end of the study, participants will be given a referral to the California Smokers' Helpline ([name]) or Kansas Tobacco Quitline ([name]).

XI. Study Questionnaires

Surveys will contain items on demographics, smoking measures, tobacco measures, physiological measures, and psychosocial assessments. Given the possibility of low literacy among participants, surveys will be verbally administered along with visual cue cards.

XII. Data Management

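### Baseline NNAL is assayed but is not among the named covariates; following that list as written would cost precision in the primary comparison

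*Protocol*

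**What the plan says.** All references are to the protocol.

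- **I. Introduction, Project Summary.** The primary outcome is introduced as a change: "Changes in toxic exposure (NNAL, a primary lung carcinogen and the primary outcome", measured from baseline to week 6. The next sentence reads "Planned covariates include study site, gender, income, tobacco dependence score, and mental health symptoms". Hypothesis 1 expects that "toxicant exposure from baseline to week 6 will be significantly lower in the EC group compared to the assessment-only group". None of these sentences names a model.
- **Sample Size paragraph.** The wording differs: "we powered primary outcomes for end-of-treatment analyses using an average of effects". The data were simulated "using the same correlation structure of assessments over time as observed in a previous study", but the correlation itself is not printed. The result is given as "With a median effect of -0.37 ($SD=0.11$) across 1000 data sets", with power above 0.82 for 180 participants and an allowance for up to 20% attrition.
- **VIII. Laboratory Procedures and Sampling, Urine sampling.** Urine is collected at three visits, but "only baseline and week 6 urine will be sent for testing", with week 2 urine substituted when the week 6 sample is missing. A baseline NNAL value is therefore planned for every participant.

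**The concern.** A participant's own baseline NNAL can be expected to predict week 6 NNAL better than most other variables the trial collects. The protocol goes as far as naming covariates, and it names five, but not this one. An analysis plan written from that list could carry the omission forward.

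Two things would be at stake. The first is the standard error of the primary contrast, in a 2:1 trial with 60 controls and a stated power only just above 0.82. The second is sensitivity to chance imbalance in baseline NNAL. An unadjusted change score over-corrects for such an imbalance whenever r is below 1, and a week 6 comparison without baseline does not correct for it at all.

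**Working it through.** **Inputs from the protocol.** d = 0.37, taken as printed; 120 e-cigarette and 60 control participants; 20% attrition, leaving 96 and 48; stated power above 0.82.

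**Assumptions, because the protocol does not give them.** Two-sided alpha of 0.05; equal variances at both times; d expressed in week 6 SD units; r from 0.3 to 0.9. The five listed covariates are ignored.

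**Formulas.** The standard error per SD unit is se = sqrt(1/n1 + 1/n2):

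- 120:60: sqrt(1/120 + 1/60) = 0.158
- 96:48: sqrt(1/96 + 1/48) = 0.177

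The SD is multiplied by a factor f that depends on the analysis:

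- week 6 value only: f = 1
- change score without baseline: f = sqrt(2(1 − r))
- week 6 value adjusted for baseline: f = sqrt(1 − r²)

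Power is approximately Φ(d/(f × se) − 1.960). The variance ratio of adjusted to change score is (1 − r²)/(2(1 − r)) = (1 + r)/2.

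**The plan's own figure.** With no use of baseline (f = 1), two-sided power is 0.648 at N = 180 and 0.553 at N = 144. One-sided it is 0.757 and 0.673. None of these reaches 0.82, so the simulation appears to have used the correlation over time in some way. Power of 0.82 requires d/(f × se) = 1.960 + 0.915 = 2.875:

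- N = 180: f = 0.37/(0.158 × 2.875) = 0.814. This needs r = sqrt(1 − f²) = 0.58 with adjustment, or r = 1 − f²/2 = 0.67 with a change score.
- N = 144: f = 0.728. This needs r = 0.69 with adjustment, or 0.735 with a change score.

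Both analyses reach 0.82 at a plausible r. The stated power is neither reproduced nor refuted, and it does not reveal which analysis was simulated.

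**Power at 96:48.**

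| r | Week 6 only | Change score | Baseline-adjusted | Variance saved against change score |
|---|---|---|---|---|
| 0.3 | 0.553 | 0.424 | 0.593 | 35% |
| 0.5 | 0.553 | 0.553 | 0.676 | 25% |
| 0.7 | 0.553 | 0.771 | 0.834 | 15% |
| 0.8 | 0.553 | 0.911 | 0.937 | 10% |
| 0.9 | 0.553 | 0.997 | 0.998 | 5% |

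Example at r = 0.7: the change score has f = sqrt(0.6) = 0.775, and the adjusted analysis has f = sqrt(0.51) = 0.714. A simulation of 4,000 data sets per setting gave 0.755 against 0.815 at r = 0.7, and 0.538 against 0.656 at r = 0.5. Gaps of 6 and 12 points agree with the table.

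**If d is in change-score SD units instead.** Change-score power at 96:48 is 0.553 at every r. Adjustment multiplies the SD by sqrt((1 + r)/2) and gives 0.738, 0.676, 0.622 and 0.574 at r = 0.3, 0.5, 0.7 and 0.9.

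**Chance imbalance at 120:60.** The SD of the baseline difference between arms is 0.158 SD. An imbalance of that size shifts a change-score contrast by (1 − r) × 0.158. That is 0.079 SD at r = 0.5 (0.079/0.37 = 21% of the effect) and 0.047 SD at r = 0.7 (13%).

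**The case against.** The strongest answer is that the protocol does not exclude baseline NNAL. The verb *include* leaves the covariate list open. In a model with baseline and follow-up values, baseline is often treated as part of the model and not as one of the additional covariates. The full model may also sit in an analysis plan that is not shown. All of this stands, and it is why the loss can only be stated conditionally.

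A reader might infer from the Project Summary that an unadjusted change-score test is fixed. It is not. Saying that changes will be measured describes the outcome, and a covariance or repeated-measures model also estimates a difference in change. The Sample Size paragraph speaks of end-of-treatment analyses. That wording does not remove the concern, however: a week 6 comparison without baseline has power of 0.55 at 96:48 whatever r is.

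A reader might also infer that the stated power is credible only if the baseline correlation is fully exploited. That fails as well, because a plain change score reaches 0.82 at r = 0.67 (N = 180) or 0.735 (N = 144).

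The gain also shrinks as r rises. Under the assumptions above, r = 0.5 does not deliver the stated power with either analysis (0.77 at best, adjusted, N = 180), so the larger gains in the table sit less easily with the plan's own figure. If the printed SD of 0.11 is read as the sampling SD of the effect at 96:48, r would be about 0.78 (adjusted) or 0.81 (change score), and the gain is only 2 to 3 points. Study site and dependence score may recover part of the precision too. These points limit the size of the concern, but none of them makes the omission useful.

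**Conclusion.** The point holds in conditional form. The protocol names five covariates for an outcome described as change in NNAL and does not name baseline NNAL, which it plans to assay. If the named list is followed, the primary contrast is less precise than the same data allow, on either the change or the week 6 reading.

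At 96:48, with d = 0.37 in week 6 SD units and two-sided 0.05, the cost against a change score is about 17 power points at r = 0.3, 12 at r = 0.5, 6 at r = 0.7 and under 1 at r = 0.9. The correlation is an assumption throughout.

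This is not a finding of bias: randomisation makes baseline imbalance a matter of chance. Nor is it a finding that the power statement is wrong. Section IX lists "creatinine mg/mL, nitrosamine 4-(methylnitrosamino)-1-(3-pyridyl)-1-butanol (NNAL) pg/mL", and nothing says NNAL will be left uncorrected for creatinine. Creatinine normalisation is a separate question and no part of this point.

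**What to change.** Add baseline NNAL to the planned covariates and say that the primary model compares the arms on NNAL at week 6, or on its change, adjusted for baseline NNAL on the same scale as the outcome. With baseline in a linear model, the two outcomes give the same treatment estimate, so the wording about change can stay. State likewise that each Aim 2 scale is adjusted for its own baseline value.

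The cost is one or two sentences in the protocol, repeated in the analysis plan. No new samples, visits or participants are needed. If the analysis plan already contains this adjustment, the change only aligns the protocol with it.

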This study is a randomized controlled trial using a 2:1 study randomization ratio. The treatment group will receive an e-cigarette and nicotine pods for six weeks and are encouraged to make a complete switch from combustible cigarettes to e-cigarettes. The study will consist of three in-person visits (baseline, week 2, and week 6) in which measurements are conducted and behavioral support is provided to the e-cigarette group. Phone calls will be scheduled between the visits (week 1 and week 4) to confirm appointments, collect data on tobacco use, and to support switching to e-cigarettes (e-cigarette group only).

[figure not shown]

Figure 1. Study Timeline.

Informed Consent. The informed consent will be reviewed by having the researcher read the consent form out loud. The participant will be given time to read the informed consent form and ask questions. It will be made clear in the consent form that the participant has the option to take more time to consider their desire to participate in the study and reschedule at a later date, or to decline to participate at any point. The study begins once the participant signs the consent form, indicating understanding of the procedures, requirements, and consent.

Incentives. Participants will be compensated for their time during the lab visits at escalating increments of \$20 at baseline, \$40 at week 2, and \$60 at week 6, totaling up to \$120. Participants in the e-cigarette group are instructed that full compensation is contingent upon bringing back their used and unused pods to their next visit. At week 2 and week 6, \$20 of compensation is contingent upon bringing back pods. Those in the e-cigarette group have the opportunity to participate in a follow-up phone assessment six months after enrollment, entailing an additional \$20 compensation.

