Study E-cigarettes. Participants in the e-cigarette group will be provided JUUL, a nicotine-salt based e-cigarette (see Figure 2). Participants will have the flavor selection of Virginia tobacco, cool mint, menthol, or mango pods containing .07 mL nicotine (5% nicotine). Pod use will be tracked using the Pod Count Form, requiring participants to bring to lab visits all used, unused, and partially used pods. Pods will be distributed based on cigarette use, and determined using the Pod Count Calculation Form. Education about switching will be verbally provided to the e-cigarette group. Participants will engage in motivational enhancement-based action planning and will receive JUUL usage instructions. Participants in the e-cigarette group will be provided a compatible wall adapter to ensure proper charging, a device carrying case, Q-tips to clean the device as needed, and a gallon Ziplock bag to store used pods.

Figure 2. JUUL electronic cigarette. Reprinted from *JUUL Labs, Inc*, Retrieved December 9, 2018, from www.juul.com. Copyright 2018.

VII. Participant Retention

Participant retention will be maintained by using a variety of contact methods including call, text, email, physical letter in the mail, and reaching out to emergency contacts. No more than six contact attempts, of various forms, will be made. Contacting emergency contacts and sending a letter will be the last efforts made to contact an unreachable participant. Additionally, participants will be sent postcards reminding them of the day and time of their next lab visit, and appointment reminder cards will be given out at the baseline and week 2 visit reminding about upcoming phone calls.

Lab visits will have pre-determined time windows. The week 2 visit can be scheduled up to one week before or after the originally scheduled date of two weeks after the baseline visit. The week 6 visit can be scheduled up to four weeks before or after the originally scheduled date of six weeks after the baseline visit. Ripple protocol details the scheduling protocol.

VIII. Laboratory Procedures and Sampling

Data from biological measurements and samples will be recorded on paper and/or in REDCap.

The table below shows the equipment used for the biological measures, and timepoints taken.

Measure	Equipment	Baseline	Week 2	Week 6
Carbon Monoxide	coVita Bedfont Micro+ Smokerlyzer®	X	X	X
Systolic Blood Pressure, Diastolic Blood Pressure, and Pulse	Omron® BP742N 5 Series Upper Arm Blood Pressure Monitor	X	X	X

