Height	Health o meter® 500KL	X		

	Professional Digital Scale			
Weight	Health o meter® 500KL Professional Digital Scale	X		X
Spirometry: FVC, FEV1, FEV1/FVC%, PEF, and FEF25- 75%	Futuremed® Discovery-2™ Desktop Spirometer	X	X	X
Saliva (10 San Diego participants)	Saliva collection aid (straw): SB-WS No.61/524,096 Collection tube: Wheaton 1.8 mL yellow cap collection tube	X		X
Nasal Swab (20 Kansas City Participants)	Leukosorb tubes, Q-tips, saline	X		X
Urine	Dynarex Specimen Container 4oz. 118cc reorder No. 4253 Aliquots: Wheaton 20 ml disposable scintillation vials	X	X	X

Table 2. Biological measures, timepoints, and equipment for Project Switch.

CO measurement. Exhaled breath samples will be taken at all visits for carbon monoxide (CO), a by-product of smoke, using a Bedfont Micro+ Smokerlyzer. At baseline, CO measurement will be taken to confirm eligibility. A carbon monoxide level over 5ppm verifies smoking status. A carbon monoxide level 5ppm or lower at baseline makes a person ineligible to participate in the study. Participants will be allowed the opportunity to re-screen two weeks later.

Blood pressure. Systolic and diastolic blood pressure will be measured for screening purposes and throughout the study using a digital blood pressure cuff. If, at the baseline or week 2 visit, a participant's systolic blood pressure is greater than or equal to 160 mm Hg or their diastolic blood pressure is greater than or equal to 105 mm Hg, they will not be eligible to participate or continue participating in the study. Pulse will also be measured but not as an exclusion criteria. Participants who are ineligible at baseline due to uncontrolled blood pressure will be allowed the opportunity to re-screen two weeks later.

Height and weight. A medical scale will be used for a one-time measure of height. Weight will be measured at baseline and week 6 visit, with shoes removed.

Spirometry. Lung function will be measured at all lab visits using a Discovery-2 SpiroVision spirometer. At each session, participants will complete a minimum of three maneuvers (depending on the quality) consisting of a strong exhale and a strong inhale.

Participants will be given a mouthpiece at baseline that will be stored and used at subsequent visits. Participants will be given the option to manually hold their nose closed or to apply a nose clip.

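### Aim 3 calls consumption change in the e-cigarette group cotinine-verified, but that group is supplied with nicotine, so cotinine alone cannot show whether a participant smokes, vapes or does both

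*Protocol*

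**What the plan says.** The purpose of Aim 3 (Protocol, section I) is "To understand patterns of tobacco product consumption among smokers switching to electronic cigarettes". In the EC group it will examine "Changes in tobacco product consumption (cotinine-verified), subjective effects of smoking, and levels of tobacco dependence from baseline to week 6", and then look for baseline predictors of the patterns found. Cotinine is the only verifier named there.

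Section VI describes what that group is given: "The treatment group will receive an e-cigarette and nicotine pods for six weeks". Under Study E-cigarettes, the listed pods contain 5% nicotine, no nicotine-free option appears, and "Pods will be distributed based on cigarette use, and determined using the Pod Count Calculation Form". The same paragraph states that "Pod use will be tracked using the Pod Count Form".

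Section VIII describes a second marker: "Exhaled breath samples will be taken at all visits for carbon monoxide (CO), a by-product of smoke". For baseline eligibility it adds: "A carbon monoxide level over 5ppm verifies smoking status". The urine assays in section IX begin "Urine: cotinine ng/mL, creatinine mg/mL" and continue with NNAL and 3-hydroxycotinine. Timeline followback is scheduled at baseline, week 2 and week 6 (section X). The Project Summary lists change in CO and NNAL as exposure outcomes. No section gives CO, timeline followback or pod counts the task of verifying consumption under Aim 3.

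**The concern.** Cotinine is a reasonable check on tobacco use when cigarettes are the main source of nicotine. In this arm the intervention supplies a second source, scaled to the first. Replacing cigarettes with pods need not lower cotinine, and a participant who uses both products can have the same value as one who has switched completely.

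Aim 3 is about these patterns and their predictors. If the analysis follows the text, a self-report of exclusive EC use would be presented as biochemically verified when the marker could not have contradicted it. Predictors of switching would then partly be predictors of how people report their smoking.

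**Working it through.** The protocol gives no figure to reproduce here, so the check is mainly a comparison of its statements, followed by a simple bound.

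**What each marker can separate.** That cotinine is a nicotine metabolite is general pharmacology, not a statement in the protocol. That CO is a by-product of smoke, and that the pods contain nicotine, is stated in the protocol.

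| Use at week 6 | Nicotine source | Cotinine | CO |
|---|---|---|---|
| Cigarettes only | cigarettes | present | raised by recent smoking |
| Both products | cigarettes and pods | present | raised by recent smoking |
| EC only | pods | present | no smoke source |
| Neither | none | falls away | no smoke source |

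Cotinine separates the last row from the other three. It does not separate those three from each other, and the 3-hydroxycotinine assay has the same limit because it also derives from nicotine. CO separates the first two rows from the third, subject to recency and amount of smoking. Pod counts and timeline followback are needed to tell the first row from the second.

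**Bound on cigarette intake.** Let T be week 6 cotinine divided by baseline cotinine. Write T = c + e, where c is the part from cigarettes and e the part from pods, both as shares of baseline nicotine. Since c ≥ 0 and e ≥ 0, it follows that 0 ≤ c ≤ T. For an illustrative smoker of 20 cigarettes a day:

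- T = 1.0 gives 0 to 20 × 1.0 = 20 cigarettes a day.
- T = 0.5 gives 0 to 20 × 0.5 = 10 cigarettes a day.

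The bound rests on four assumptions:

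- Cotinine is proportional to total nicotine.
- Nicotine per cigarette is the same at both times.
- Cigarettes and pods are the only sources of nicotine.
- Pod use can supply as much as the fraction T. The protocol gives no absorption figure, so this is not established.

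The third assumption is only approximate, because the exclusion criteria bar primary or equal use of other tobacco products, not all use. If the second or third fails, the upper limit moves; the lower limit of zero does not. Within these assumptions cotinine can cap cigarette intake, but while pods are in use it cannot confirm that intake is zero.

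**The case against.** The strongest reply is that Aim 3 does not say what is being criticised. It speaks of tobacco product consumption, which can include e-cigarettes, and it never says that cotinine will verify abstinence from cigarettes. On that reading the bracketed term is correct, and the way CO, timeline followback and pod counts are combined can be left to a statistical analysis plan, which is not among the documents at hand.

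Part of this stands. Cotinine is a valid check on total nicotine and should stay. The label is also a short parenthesis in a summary, not a full analysis definition. But the aim concerns patterns of use among people moving between two nicotine products, and a total cannot verify a pattern. The protocol itself names the verifier, so this is a stated choice that does not fit the arm. An analysis plan written to Aim 3 would inherit it.

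A reader might infer that the trial cannot distinguish smoking from vaping at all. The protocol does not support that: CO is taken at all three visits, use is recorded by timeline followback, and pods are returned and counted. The data are planned; what is missing is their link to Aim 3.

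**Conclusion.** The concern holds in a limited form. In an arm supplied with nicotine pods, cotinine checks total nicotine exposure only. Described as the verifier of consumption change, it claims more than it can show about which product was used. This rests on the pharmacology of cotinine and on the protocol's own description of the pods.

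The reach is one descriptive aim with no directional hypothesis or power statement of its own. A reader might infer that the primary result is at risk; it is not, because the NNAL comparison between arms does not depend on how Aim 3 verifies use.

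A reader might also try to size the problem from the shares of fuller and partial switchers in the Sample Size paragraph. Those shares are assumptions about NNAL effects, and switching more completely is not defined there as exclusive EC use. They do not count participants misclassified through cotinine, and no such count can be derived from the protocol.

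**What to change.** In Aim 3, state what each measure is used for:

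- Self-reported non-smoking or exclusive EC use at week 6 is verified by exhaled CO, read with timeline followback and pod counts.
- If the protocol's own level is used (5 ppm or lower counted as consistent with not smoking), write it in as a follow-up analysis definition. At present it is stated only for baseline smoking status.
- Cotinine is reported as the measure of total nicotine exposure.
- The size of a partial cigarette reduction is labelled as self-reported.

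NNAL should not serve as the classifier, because it is the primary outcome. CO is itself a listed exposure outcome, so its change should not be presented as a finding across groups that were defined by CO.

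The cost is wording and one analysis definition; no new sample, visit or assay is needed. The drawback is that CO reflects recent smoking and may miss light smoking, so some continued smoking would still pass as exclusive EC use. The text should say so.
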